1.2 Research Rationale and Supporting Evidence

Among LE devices, Intrapulmonary percussive ventilation (IPV) devices have been in use for more than 25 years and are used widely in the acute care, post-surgical, and homecare setting. Such devices provide both LE and airway clearance therapy (ACT) for patients with obstructive and/or restrictive lung diseases and conditions. The safety and efficacy of IPV have been demonstrated in clinical and laboratory studies.^[12-34]

The MetaNeb® System is an LE expansion modality that incorporates all the physiological effects of IPV while providing additional therapeutic advantages intended primarily to more effectively treat or prevent pulmonary atelectasis. Equipment consists of a pneumatic compressor that delivers continuous high-frequency oscillation (CHFO) and positive expiratory pressure (CPEP) to 1) facilitate clearance of mucous from the lungs; 2) provide lung expansion therapy and; 3) enhance delivery of aerosol therapy. This “triple” mode device can provide aerosol therapy while alternating between CPEP for lung expansion and CHFO for airway clearance. Supplemental oxygen therapy may also be delivered when used with compressed oxygen. The MetaNeb® System has been cleared to market by the FDA based on substantial equivalence to IPV. Clinical studies of The MetaNeb® System, however, are limited. The only peer-reviewed publication to date is a case report concerning a patient who on her 17th hospital day, following an adverse medication reaction, developed severe atelectasis secondary to toxic epidermal necrolysis (Stevens - Johnson Syndrome). After initiation of therapy with The MetaNeb® System, atelectasis was completely resolved by hospital day 21. The patient was discharged on hospital day 25 without further pulmonary complications.^[35] In addition to this publication, however, a number of abstracts and other reports have been presented or published. An abstract presented at the American Association for Respiratory Care (AARC) Congress in 2009, found that patients participating in a progressive pulmonary protocol in an oncologic intensive care unit and who received LE therapy with either IPV or The MetaNeb® System had significantly better post- therapy chest x-ray results compared with patients treated with The Vest® System and EZ PAP.^[35] An earlier case study report presented at the AARC Congress in 2006 described an 80-year-old post-thoracoscopic surgical patient in respiratory distress. The patient was treated with The

Hill-Rom®	Evaluation of a practice change to include The MetaNeb® System to reduce postoperative pulmonary complications	Page 12 of 31
CBI	8 September 2016	Rev C Protocol #: CR-RR2015-001

MetaNeb® System, expectorated large amounts of tenacious secretions, and after only 2 treatment sessions had improved breath sound. Chest radiographs showed improved aeration and there was a reduction in oxygen requirement.^[37] In a long-term care treatment protocol with intubated or tracheostomised patients on MV, patients were treated with The MetaNeb® System for 10 minutes every 6 hours until decannulation or discharge. Quality improvement results showed improvement in the percentage of patients weaned from MV along with a decrease in the need for bronchoscopy.^[38] Two more recent studies have been presented at conferences and await full-text publication. Patel et al. reported on a randomized parallel study comparing outcomes in 32 adult CF patients with severe pulmonary exacerbations and admitted for IV therapy. Patients were randomized to treatment with either The MetaNeb® System or The Vest® System for up to 14 days. In this setting, results were positive but comparable.^[39] Morgan, et al. investigated the feasibility, safety and efficacy of CHFO administered via The MetaNeb® System to 59 invasively ventilated pediatric patients, between 2007-2012. A total of 528 treatments were evaluated. Preliminary results support safety and feasibility and suggest that CHFO may be beneficial by improving lung compliance in patients with secretion-induced atelectasis.^[40]

1.3 Rationale for the Proposed Study

Preliminary and anecdotal evidence suggests that use of The MetaNeb® System may be effective in postoperative patients prone to atelectasis and PPCs. The proposed study is intended to evaluate the effectiveness of this therapy in reducing the incidence of these complications in comparison to standard treatment.

2.0 Study Objectives

The primary objective of this study is to determine if a therapy regimen including treatment with The MetaNeb® System has a positive impact on the rate of pulmonary complications that occur in high risk post-operative patients.

3.0 Study Design

3.1 Overview of Study Design

3.1.1 Design:

This is a non-randomized facility level pre-post intervention study conducted in two stages for the primary purpose of evaluating the effect of The MetaNeb® System on postoperative pulmonary complications in high risk patients undergoing thoracic and

Hill-Rom®	Evaluation of a practice change to include The MetaNeb® System to reduce postoperative pulmonary complications	Page 13 of 31
CBI	8 September 2016	Rev C Protocol #: CR-RR2015-001

abdominal surgeries. The study will be conducted in two to four (2-4) tertiary academic medical facilities in the US that have not previously used The MetaNeb® System in post-thoracic, post-aortic, or post-upper abdominal surgery patients. After assessing outcomes during a baseline period, therapy with The MetaNeb® System will be introduced and incorporated into the respiratory care treatment regimens and outcomes will be assessed after the change in practice.

3.1.2 Procedure:

In Stage I of the study, a retrospective review of medical records for post-surgical patients, who received STANDARD THERAPY as defined by current hospital and Respiratory Care department policies and procedures. This will be a retrospective data collection only.

The purpose of study Stage I is to estimate the incidence of postoperative pulmonary complications in post-surgical patients receiving standard of care per hospital and Respiratory Care department procedures and policies. Data collected in Stage I will include data from the medical records of 200 randomly selected, eligible patients treated during the year prior to the CHANGE IN PRACTICE. This allows for inclusion of patients from the seasonally consistent time period as well as those from most recent time period, during which care practices are most similar.

In Stage II, a CHANGE IN PRACTICE will be made and patients will receive standard care with the addition of therapy with The MetaNeb® System. Other standard airway clearance and lung expansion therapies typically delivered by Respiratory Therapy will not be delivered during Stage II. During Stage II, data from approximately 200 patients will be collected from the medical records across the 3 sites.

Demographic, clinical & outcome data will be collected for eligible patients during the two stages of the study. Study staff will collect data from the medical records, following a protocol determined schedule.

Pre-surgery data will be collected for eligible patients in both stages. In both Stage I and Stage II, outcomes will be tracked for each day from the time of the post-surgical admission to the hospital unit through post-surgery day seven (7). Additionally, hospital length of stay (LOS) and total ICU LOS will be determined based on documentation of admission and discharge dates and times for all days of hospitalization. Length of time on mechanical ventilation (LOMV) will be determined based on documentation of initiation and discontinuation dates and times for all days

Hill-Rom®	Evaluation of a practice change to include The MetaNeb® System to reduce postoperative pulmonary complications	Page 14 of 31
CBI	8 September 2016	Rev C Protocol #: CR-RR2015-001

of hospitalization. LOS and LOMV data will be collected from the medical record upon discharge from the hospital. Hospital records will also be reviewed after 30 days to determine if readmission to the hospital occurred for any study patients.

A timeline showing data procedures and collection points is included as Table 1 Study Observations Table.

The estimated study enrollment is 200 patients in both stages. However, an adjustment in sample size may be made based on the incidence rate for post-operative pulmonary complications in Stage I, to allow for a robust estimate and assessment of the effect of therapy with The MetaNeb® System.

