3.5 Statistical Methods and Analysis

3.5.1 Sample Size Estimation:

This study is designed to provide information on the benefits of the addition of the MetaNeb® System in reducing the incidence of postoperative pulmonary complications (PPCs) in high-risk subjects undergoing high-risk surgical procedures (upper abdominal, thoracic, aortic). The study will be conducted in 2 stages:

- Stage I: To update/confirm the estimate of the current incidence of PPC's with current Standard of Care Practice. Recent published articles suggest incidence rates between 5%-15%, depending on the patient population and type of surgery. This stage of the study will be a retrospective pre-intervention observational period, conducted at 2 - 4 hospitals/sites, with no intervention in the patients' post-surgical

Hill-Rom®	Evaluation of a practice change to include The MetaNeb® System to reduce postoperative pulmonary complications			Page 22 of 31
	CBI	8 September 2016	Rev C	Protocol #: CR-RR2015- 001

management. Data from approximately 200 subjects will be collected. The incidence rate will be calculated, along with a 95% confidence interval.

- Stage II: To assess the impact of the MetaNeb® System on the incidence of PPC's. This stage of the study will be a prospective post-intervention period conducted in the same 2 - 4 hospital sites with an intervention involving use of the MetaNeb® System in addition to Standard of Care Practice.

3.5.2 Statistical Analysis:

- Summary statistics and data listings will be provided.
- Demographic data will be summarized. For continuous type data (e. g. Age), descriptive summary statistics (N, mean, median, standard deviation, min, and max) will be presented. For categorical variables (gender, race, etc.) the number and percent of patients in each category will be provided.

Primary Endpoints:

The incidence of significant postoperative pulmonary complications (as defined in section 3.3) along with 95% confidence interval will be generated. Additionally, the incidence rates will be summarized for various demographic subsets, by surgery type, and for different population subsets. The descriptive summary statistics for the subsets may be presented side-by-side for ease of comparison. The specific subsets to be summarized will be described in a separate document (the statistical analysis plan).

Secondary Endpoints:

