### **6.1.2 Accounting of Subjects**

Numbers (and percentage) of subjects enrolled in Stage I and Stage II, will be presented by site and overall.

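### The stage comparison is open to case-mix bias: neither stage fixes its shares by surgery type or site, and the SAP plans only crude pooled PPC proportions

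*Protocol*

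**What the plan says.** **Selection.** Protocol 3.1.2 describes Stage I as "records of 200 randomly selected, eligible patients treated during the year prior to the CHANGE IN PRACTICE". For Stage II it says: "During Stage II, data from approximately 200 patients will be collected from the medical records across the 3 sites". On totals, "The estimated study enrollment is 200 patients in both stages", but "an adjustment in sample size may be made based on the incidence rate for post-operative pulmonary complications in Stage I". Protocol 3.5.1 says that Stage II is "conducted in the same 2 - 4 hospital sites" as Stage I. SAP 1 and 3 repeat this design. No number, share, matching rule or consecutive-enrolment rule by surgery type or site appears in either document.

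**Risk.** Protocol 1.1 counts the type of surgery among the key factors for PPC. Protocol 3.5.1 adds: "Recent published articles suggest incidence rates between 5%-15%, depending on the patient population and type of surgery". Protocol 3.1.2 defines comparator care by each hospital's own policies, and Protocol 3.3 leaves the white-count limit for pneumonia to the site and lets the site set its own temperature limits.

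**Analysis.** SAP 6.3 presents the PPC proportion with a 95% confidence interval, and the incidence of its four components. It names no between-stage method, stratification or adjustment. SAP 6.1.2 says: "Numbers (and percentage) of subjects enrolled in Stage I and Stage II, will be presented by site and overall". That covers counts, not outcomes. Protocol 3.5.2 commits to PPC incidence by surgery type and leaves the list of subsets to the SAP. The SAP lists none, and surgery type is absent from the baseline table in SAP 6.1.3. Protocol 3.5.2 nevertheless compares the stages to find associations attributable to the device.

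**The concern.** A facility-level pre-post design is useful because each hospital serves as its own control. That holds only if the comparison is made within hospital, or if the hospitals and their surgical case mix carry the same weight in both stages. This plan secures neither.

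The stages also select patients by different routes. Stage I is a chart draw for which a consent waiver is requested. Stage II requires individual consent (Protocol 5.1), and its primary population drops patients who did not receive the device (SAP 6.2). The Stage II mix therefore depends on who consents and who is treated. The random Stage I draw does not control that.

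If the mix moves towards lower-risk surgery or lower-rate hospitals, the pooled rate falls with no change in care. If it moves the other way, a real benefit can be hidden. The bias does not shrink with more patients. Because the SAP shows neither surgery type by stage nor PPC by surgery type, a reader of the planned tables could not separate a change in surgical mix from a device effect.

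**Working it through.** **Inputs from the documents.** About 200 patients per stage (Protocol 3.1.2). Two-sided 5% error rate (SAP 6). Published incidence of 5% to 15% (Protocol 3.5.1). Three surgery types (Protocol 3.2.1). Two to four sites, with three named in the Stage II sentence (Protocol 3.1.1 and 3.1.2). There is no power or effect-size figure to reproduce: SAP 5 says that no formal sample size determination was made.

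**Assumptions.** The risk in each stratum and the shares in each stage are not in the documents. Placing strata at 5%, 10% and 15% uses the whole published spread and is an outer bound.

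**1. Bias in the pooled rate, no device effect.** Pooled rate = sum of (share × stratum risk).

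- Stage I, equal thirds: (5 + 10 + 15)/3 = 10.0%.
- Stage II at 50/30/20%: 2.5 + 3.0 + 3.0 = 8.5%. Bias −1.5 points, an apparent 15% relative reduction (1.5/10.0).
- Stage II at 20/30/50%: 1.0 + 3.0 + 7.5 = 11.5%. Bias +1.5 points, an apparent 15% increase.
- Narrower risks of 7.5%, 10% and 12.5%, at 50/30/20%: 3.75 + 3.0 + 2.5 = 9.25%. Bias −0.75 points.

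**2. False-positive rate of a crude comparison.** SE = √[p₁(1−p₁)/200 + p₂(1−p₂)/200]; rate ≈ Φ(−1.96 + d/SE) + Φ(−1.96 − d/SE), where d is the absolute bias.

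- 10.0% v 8.5%: SE = √(0.000450 + 0.000389) = 0.0290; d/SE = 0.52; rate ≈ 0.075 + 0.007 = about 8%. The 95% half-width is 1.96 × 0.0290 = 5.7 points.
- 10.0% v 9.25%: SE = √(0.000450 + 0.000420) = 0.0295; d/SE = 0.25; rate ≈ 0.044 + 0.013 = about 6%.

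**3. How large a shift would be needed.** Take two strata at 15% and 5%, again the outer bound, with no device effect. Each 10-point fall in the high-risk share lowers the pooled rate by 0.10 × (15 − 5) = 1.0 point. Simulation with 40,000 runs and 200 per stage gave:

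| High-risk share, Stage I → II | Pooled rates | Crude test, p<0.05 | Stratified CMH test, p<0.05 |
|---|---|---|---|
| 50% → 50% | 10% v 10% | 4.9% | 5.0% |
| 60% → 40% | 11% v 9% | 9.7% | 4.9% |
| 70% → 30% | 12% v 8% | 25.6% | 5.1% |
| 80% → 20% | 13% v 7% | 51% | 4.9% |
| 90% → 10% | 14% v 6% | 77% | 5.1% |

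The Cochran-Mantel-Haenszel (CMH) test stratified on the mix variable stays near 5% throughout. With a complete 100% → 0% shift no stratum overlaps, and no stratified comparison is possible.

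**4. Sparseness of a full cross-classification.** Three sites by three surgery types make 9 cells: 200/9 ≈ 22 patients per cell per stage, and about 2 events per cell at 10% incidence.

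**The case against.** The plan has real protections. The same hospitals serve in both stages. Stage I is a random sample over a full year, chosen for seasonal and practice comparability, and should reproduce the eligible mix of the records sampled. Eligibility is limited to high-risk open cases with an incision at or above the umbilicus, which may narrow the spread of risk between strata. Site counts are reported, and the protocol promises incidence by surgery type. A 1.5-point bias is also small beside a 5.7-point half-width.

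These points limit the size of the problem but do not remove it. The random draw governs only the Stage I mix, site counts carry no outcomes, and the SAP does not carry out the promised surgery-type summary.

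Three stronger readings are tempting, and the documents do not support them:

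- A reader might infer that the plan expects a threefold PPC difference between sites. The 5% to 15% range is a spread across published articles, tied to patient population and type of surgery. Site is not mentioned. The case for site rests on local care policies and site-defined pneumonia limits, which give no figure.
- A reader might infer that Stage II is filled by whichever hospitals or services enrol fastest. The documents are silent on how it is filled.
- A reader might infer that a mix shift alone would probably produce a significant result. Even at the outer-bound risks, that becomes about as likely as not only at a shift near 60 percentage points.

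**Conclusion.** The concern holds as a gap in analysis and reporting. No share by surgery type or site is fixed in either stage, the two selection routes differ, and no adjusted or stratified stage comparison is specified, although the protocol intends to attribute differences to the device. The direction of any bias is unknown.

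For the moderate three-stratum shift the bias is 0.75 to 1.5 points and the crude false-positive rate about 6% to 8%, against a nominal 5%. Larger shifts would do more harm, but nothing in the documents says that they will occur. All these figures rest on assumed stratum risks and shares, and smaller risk contrasts reduce the bias in proportion. This should be corrected because the remedy is cheap; it does not show that the design must fail.

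**What to change.** **SAP 6.3.** Pre-specify as the main stage comparison the Stage II minus Stage I difference in PPC risk, with a 95% confidence interval, adjusted for surgery type and site. Either of two methods would serve; name one in advance:

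- a Mantel-Haenszel risk difference over surgery-type and site strata; or
- standardisation to the Stage I mix, from a model with stage and main effects of site and surgery type, which avoids the sparse cells of a full cross-classification.

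Keep the crude proportions alongside, and add PPC by surgery type and by site for each stage. This also meets the protocol's own commitment.

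**SAP 6.1.3.** Tabulate surgery type by stage.

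**Optional, Protocol 3.1.2 and SAP 1 and 3.** Draw the Stage I charts stratified by site and surgery type, with stated numbers. This costs little. Per-site targets for Stage II are a further option, but could slow enrolment at a low-volume hospital, and the adjusted comparison does not depend on them.

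**Cost.** Slightly more analysis work and no new data: surgery type is already collected (Protocol 3.4.1) and enrolment is already counted by site. The limitation is that a stratum present in only one stage contributes nothing to a stratified comparison. The SAP should say how such strata will be reported.

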3.1.3 Product Description

The product added in Stage II, the CHANGE IN PRACTICE phase is The MetaNeb® System, a therapeutic device that provides airway clearance and lung expansion therapy. The MetaNeb® System is a marketed product, indicated for mobilization of secretions, lung expansion therapy, the treatment and prevention of pulmonary atelectasis and also has the ability to provide supplemental oxygen when used with compressed oxygen. The system has three therapy modes:

- CHFO (Continuous High Frequency Oscillation) – delivers aerosol therapy while providing oscillating pressure pulses to the airway
- CPEP (Continuous Positive Expiratory Pressure) – delivers aerosol therapy while providing continuous positive pressure to help hold open and expand the airways
- Aerosol – for delivery of aerosol only. In this mode, CHFO and CPEP are not available

3.1.4 Treatment Protocol(s):

Stage I: STANDARD THERAPY period:

In Stage I of the study, a retrospective review of medical records for post-surgical patients, who received STANDARD THERAPY as defined by current hospital and Respiratory Care department policies and procedures. This will be retrospective data collection only. The purpose of Stage I is to estimate the incidence of postoperative pulmonary complications that occur in postsurgical patients who receive standard therapy.

Hill-Rom®	Evaluation of a practice change to include The MetaNeb® System to reduce postoperative pulmonary complications	Page 15 of 31
CBI	8 September 2016	Rev C Protocol #: CR-RR2015-001

Respiratory Care therapies (e.g. nebulizer treatments, chest physiotherapy, etc.) that were delivered during the first seven (7) days following surgery, including delivered frequency, will be collected.

Stage II: CHANGE IN PRACTICE period:

The treatment protocol used for Respiratory Care during the CHANGE IN PRACTICE period of the Study will be that prescribed by the patient's health care team in the routine standard care of each patient. With the exception of standard airway clearance and lung expansion procedures, other components of the patients respiratory care regimen will remain the same as during the standard therapy period, however the CHANGE IN PRACTICE will incorporate the use/treatment with The MetaNeb® System as an alternative to usual airway clearance and lung expansion procedures. Use of The MetaNeb® System will follow the labeling of the device.

Respiratory Care therapies, including therapy with The MetaNeb® System, that are delivered during the first seven (7) days of Stage II, including delivered frequency, will be collected.

Exceptions to the above treatment protocols required for patient care as determined by the treating physician will be collected.

3.2 Study Population

The study population consists of adult post-surgical patients who have undergone thoracic, aortic or upper abdominal surgery who are at high risk for PPCs.

3.2.1 Inclusion Criteria:

Patients who meet all of the following criteria will be included in the study:

- Age \geq 18 years
- Post-thoracic, -upper abdominal or -aortic surgery
- Open surgical procedure
- Incision at or above the umbilicus
- High risk defined by:
 - Documented ASA class \geq 3

Hill-Rom®	Evaluation of a practice change to include The MetaNeb® System to reduce postoperative pulmonary complications			Page 16 of 31
	CBI	8 September 2016	Rev C	Protocol #: CR-RR2015- 001

OR

- Documented ASA class 2 **AND** One or more of the following:
 - Current Smoker or Smoking history within past 6 months
 - History of COPD
 - Documented Obesity and/or BMI $\geq 30 \text{ kg/m}^2$
 - Age ≥ 75

3.2.2 Exclusion Criteria:

Patients who meet any of the following criteria will be excluded (or will be exited) from the study:

- Contraindication to Continuous High Frequency Oscillation (CHFO) therapy (e.g. untreated tension pneumothorax)
- Minimally invasive or “...scopic” surgical procedure
- Spinal surgery involving a posterior approach
- Surgery for organ transplant
- Chronic invasive Positive Pressure Ventilation (PPV) therapy

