3.3 Evaluation Criteria/Effectiveness

The CHANGE IN PRACTICE therapy regimen (which includes therapy with The MetaNeb® System) will be evaluated to determine if there is a decrease in the number of patients who experience Significant Postoperative Pulmonary Complications among the group of patients treated with The MetaNeb® System. Endpoints are described below:

Primary Endpoint:

Significant Postoperative Pulmonary Complication (PPC):

One or more of the following that occurs within seven (7) days of the post-surgical admission will be considered a Significant Postoperative Pulmonary Complication (PPC)

- **Patient Requires Prolonged Mechanical Ventilation:**

Defined as patient requirement for invasive mechanical ventilation (MV) for > 24 hours (after hour 24) post-operatively. This includes patients that require re-intubation and MV after hour 24, regardless of length of time on MV in the first 24 hours postoperatively.

Hill-Rom®	Evaluation of a practice change to include The MetaNeb® System to reduce postoperative pulmonary complications	Page 17 of 31
CBI	8 September 2016	Rev C Protocol #: CR-RR2015-001

- **Patient requires prolonged respiratory support for > 24 hours from post-surgical admission**
 - Requirement for non-invasive ventilation (NIV) above patient's baseline requirement after hour 24, or continuous positive airway pressure (CPAP) above patient's baseline requirement after hour 24.
 - Requirement for O₂ therapy > 40 % FiO₂ or > 5 LPM via NC (and above patient's baseline) after hour 24 postoperatively.
- **Diagnosis of Pneumonia Within Seven (7) Days**
 - Physician documented pneumonia AND
 - Radiologists report indicating pneumonia / new or expanded infiltrate AND
 - Elevated or low Temperature (> 38° C or < 36° C, or as defined by the site) and/or elevated white count above the upper level of normal as defined by the site
- **Readmission to ICU (or transfer to an elevated level of care) for pulmonary complications within seven (7) days of the post-surgical hospital admission**

Defined as readmission to the ICU within seven days of post-surgical hospital admission or readmission to an elevated care unit such as special care or ICU step-down unit after being moved to a lower (e.g. general care) floor (e.g. patient discharged from ICU on day 4 at 0800 is readmitted to the ICU before day 8 at 0800).

Secondary Endpoints:

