## **6.2 Analysis Population**

Two analysis populations will be defined:

- FAS: The full analysis data set will contain all subjects, for whom hospital records were pulled and recorded.
- ITT: The intent-to-treat (ITT) population, a subset of the FAS, includes all subjects who satisfied all the inclusion criteria and none of the exclusion criteria. For Stage II of the study, patients who did not receive the MetaNeb® system will be excluded from the ITT population.

The ITT population will be the primary population for the analysis.

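### The exclusion criteria are undated, serve as an exit rule and define the ITT set, so a contraindication arising during therapy could remove a Stage II patient from the primary analysis

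*Protocol*

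**What the plan says.** Protocol 3.2.2, repeated in the synopsis, introduces the exclusion list with: "Patients who meet any of the following criteria will be excluded (or will be exited) from the study". Only someone already in the study can be exited, so the list also works after enrolment. No time limit is attached.

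One listed item reads "Contraindication to Continuous High Frequency Oscillation (CHFO) therapy (e.g. untreated tension pneumothorax". Another is "Chronic invasive Positive Pressure Ventilation (PPV) therapy".

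SAP 6.2 defines the ITT set as a subset of the FAS that "includes all subjects who satisfied all the inclusion criteria and none of the exclusion criteria", again without a time point, and adds: "The ITT population will be the primary population for the analysis". The FAS is wider and would keep exited patients whose records were taken, but no analysis on it is specified.

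Table 1 in Protocol 3.4 places selection before surgery, without distinguishing the stages, and has an early-termination column. Neither document says whether an exited patient stays in the ITT set, is followed to day 7, or how that patient's PPC outcome is set.

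For Stage I, Protocol 3.1.2 says: "Data collected in Stage I will include data from the medical records of 200 randomly selected, eligible patients treated during the year prior".

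**The concern.** Eligibility should be fixed by what is known before the outcome period starts. Here the same list can be applied at any time, and the primary analysis set depends on it. The protocol's own example of a CHFO contraindication is an acute state, and the population includes thoracic surgery. A Stage II patient who develops such a state while on the device meets an exclusion criterion, can be exited under Protocol 3.2.2, and then fails the ITT definition in SAP 6.2. The event that removes the patient may itself be a consequence of treatment.

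The stages are not placed alike. Stage I patients are never on the device, and the sites had not used it in these patients, so their clinical teams had little reason to judge or record a CHFO contraindication, and nobody could be exited as care unfolded. If patients removed in Stage II have a higher PPC risk than the rest, Stage II incidence falls without any benefit. This is separate from the SAP rule that "For Stage II of the study, patients who did not receive the MetaNeb® system will be excluded from the ITT population", which concerns patients never treated.

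**Working it through.** The plan gives no effect size, power or exit rate (SAP 5 reports no formal sample size determination), so there is no stated figure to reproduce. The calculation below shows scale only.

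**Inputs from the documents.** About 200 patients per stage (synopsis); PPC incidence p of 5% to 15% (Protocol 3.5.1); two-sided tests at 5% (SAP 6).

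**Assumptions.** No true effect; k patients exited, in Stage II only; q is the PPC risk among those exited. SAP 6.3 names no between-stage test, so a pooled z test is assumed.

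**Expected Stage II rate after exits:** p₂ = (200p − kq) / (200 − k).

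This is below p only when q > p. The direction therefore depends on exited patients being at higher PPC risk than average. With p = 10% and k = 4:

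- q = 1: (20 − 4)/196 = 16/196 = 8.2%, an apparent relative reduction of 18%.
- q = 0.5: (20 − 2)/196 = 18/196 = 9.2%, a reduction of 8%.
- q = 0: 20/196 = 10.2%, a slight shift against the device.

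**Chance of a false finding for the device.** Two independent binomials were enumerated (Stage I: n = 200 at p; Stage II: n = 200 − k at p₂), counting outcomes with z > 1.96 in the device's favour.

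| Exits | PPC among exited | p = 5% | p = 10% | p = 15% |
|---|---|---|---|---|
| 0 | – | 5.0%; 2.4% | 10.0%; 2.4% | 15.0%; 2.5% |
| 2 | half | 4.5%; 3.9% | 9.6%; 3.5% | 14.6%; 3.1% |
| 4 | half | 4.1%; 6.4% | 9.2%; 4.6% | 14.3%; 3.9% |
| 4 | all | 3.1%; 15.9% | 8.2%; 9.2% | 13.3%; 7.2% |

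Each cell gives the expected Stage II rate, then the chance of a false finding for the device. The first row also shows the position if later cases stay in the primary set with their outcomes counted.

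If Stage I lost the same fraction of patients with the same PPC risk, both expected rates would shift equally and the bias would cancel. The concern is that nothing ensures this.

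**The case against.** **The exit wording has an ordinary use.** Selection and Stage II consent precede surgery, yet several criteria concern the operation itself: open or scopic, site of incision, posterior spinal approach, transplant. A consented patient whose operation turns out ineligible has to leave. This stands, and it is why the wording should be limited rather than deleted. The text does not confine itself to that use.

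**Ventilator dependence.** A reader might infer that patients who cannot be weaned would also be exited. The documents do not support this. The criterion covers chronic ventilation only, naturally a pre-existing state. New postoperative ventilation is an endpoint event: "Defined as patient requirement for invasive mechanical ventilation (MV) for > 24 hours (after hour 24) post-operatively". SAP 6.1.1 codes it as a PPC. At most, the word chronic needs a clarifying date.

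**Stopping the device as leaving the study.** A reader might treat these as one event. SAP 6.4.3 lists them as alternatives, and both documents say exceptions to the treatment protocol will be collected, which points to continued data collection. The route to removal is through the exclusion criterion, not through stopping therapy.

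**Stage II only.** A reader might infer that removal cannot happen in Stage I. The criteria apply to both stages, and a chart reviewer who sees the postoperative course could screen out the same condition. This stands: the direction of bias is likely, not certain. It also shows why a common time point is needed.

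**Size.** The exit numbers are assumed. Pneumothorax is not itself a PPC component, so taking every exited patient to have a PPC is an extreme case. At p = 5% with four exits, all with a PPC, the apparent reduction is 39% (6/196 = 3.1%), but that requires four of only ten expected PPC patients to be exited by this route. It should not be read as the likely effect.

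**The FAS.** It keeps exited patients in the data, but it is not primary and has no planned analysis, so it does not resolve the problem.

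**Conclusion.** The concern holds for the CHFO criterion. Two undated rules, read together, allow a Stage II patient to be removed from the primary denominator because of an event after treatment began, and nothing in either document keeps that patient in. Handling may differ between stages, and the likely direction favours the device.

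At 10% PPC, with four exits in Stage II only and no true effect, the apparent reduction is 0.8 to 1.8 percentage points, depending on whether half or all of the exited patients had a PPC. The false-finding chance roughly doubles or nearly quadruples. With two exits, half with a PPC, it rises by at most 1.5 percentage points across the 5% to 15% range. These figures rest on assumed exit numbers that may well be too high. Severity is moderate: worth correcting before Stage II data are analysed, but not enough by itself to invalidate the comparison.

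**What to change.** In Protocol 3.2.2, the synopsis and SAP 6.2:

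1. State that exclusion criteria are judged once, on the patient's status up to the post-surgical admission, identically in both stages, and that the chronic ventilation criterion means the pre-surgical state.
2. Limit the exit wording to patients found ineligible by that time point, for example a consented patient whose operation was not open.
3. State that a patient who meets a criterion later stays in the ITT set, with outcomes taken from the medical record through day 7, discharge and day 30.

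Clinical handling of a contraindication is left to the existing documents. The cost is a few sentences and no added procedures, since outcomes already come from the medical record. The downside is that Stage II PPC incidence may look slightly less favourable.
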